## 5.6 Data Analysis

Descriptive analyses at baseline will be used to examine participant characteristics and demographic variables and compare them across the sample and by genotype, including age, sex, height, education, disease duration, disease severity, physical activity levels cognitive task performance and global cognition. Histogram and quantile-quantile plots will be generated for each variable and transformation will be used when necessary to improve the fit to normality.

**Aim 1:** The primary hypothesis that motor learning is reduced in those carrying *APOE* or *BDNF* genetic variants compared to those without *APOE*-ε4 or *BDNF*-Met66 genotypes will be tested using repeated-measures analysis of variance (ANOVA) with one within-group factor, time point (0 weeks, 2 weeks for short-term motor learning; 0 weeks, 10 weeks for long-term motor learning) and one between-group factor, genetic group (*BDNF*-Met66 group, *APOE*-ε4 group, no Met66 nor ε4 allele group) to examine changes in the primary outcome measure for walking, gait speed. The secondary hypothesis examining the effect of genotype on retention of motor learning changes will be tested using repeated-measures ANOVA with one within-group factor, time point (10 weeks, 16 weeks follow-up) and one between-group factor, genetic group to examine changes in gait speed. The secondary hypothesis examining the effect of genotype on the transfer of motor learning from the trained walking task (straight line walking at a self-selected speed) to more complex walking tasks will be tested using repeated-measures ANOVA with one within-group factor, time point (0 weeks, 10 weeks) and one between-group factor, genetic group to examine changes in gait speed for dual-task walking and peak turning velocity for turning while walking. For all analysis, unadjusted models will be used. We will consider adjusting for age, height, cognitive task performance (for dual-task) or global cognition if any of these factors are shown to be different between genotype groups.

**Aim 2:** The primary hypothesis that those carrying *APOE* or *BDNF* genetic variants will experience reduced improvement in cognitive performance in different domains compared to those with *APOE-ε4* or *BDNF-Met66* genotypes, will be tested using a repeated-measures analysis of the covariance (ANCOVA), with visit (0 weeks, 10 weeks) as the within-group factor and genetic group (*BDNF-Met66* group, *APOE-ε4* group, no Met66 nor ε4 allele group) as the between-group factor for each of the tests, with adjustment for important covariates: age, disease duration and years of education.

All analyses will be performed using commercially available software (Stata, version 14.0; StataCorp).

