## 5.0 Study Procedures

### 5.1 Study Design

To achieve these aims we will enroll thru the WPDR 30 Veterans with PD (10 subjects in each the three genotype groups: (1) at least one BDNF-Met66 allele, (2) at least one APOE-ε4 allele and (3) no Met66 nor ε4 allele) in a 10-week moderate intensity gait training program consisting of 2 times per week treadmill training with verbal cues for gait quality. Genotypes will be available thru the WPDR and recruitment will be targeted for those groups of patients.

Aim 1 will examine the association between variants in 2 genes known to affect cognition and motor learning (APOE-ε4 and BDNF-Met66), and motor improvements after gait training. Aim 2

will examine the effect of APOE-ε4 and BDNF-Met66 genetic variants on cognitive changes in response to this training program.

Participation in this study involves a total of 22 visits to the VA Puget Sound (**Table 1**). These visits will occur over approximately 16 weeks, for a total of ~28 hrs.

In the rare event that we cannot meet our targeted number, we will contact and recruit non-Veterans also enrolled in WPDR.

**Visit 1**, the baseline assessment, will include:

- 1) An interview to collect key demographic variables (such as gender, age, height, weights, etc.) as well as information about the disease, medications, etc.
- 2) A visit with a neurologist to test the severity of PD motor signs using the Movement Disorders Society Unified Parkinson's Disease Rating Scale (MDS-UPDRS).
- 3) Questionnaire to assess fall history including the number of recent falls, circumstances, causes, and associated injuries
- 4) Questionnaire about physical activity levels using the International Physical Activity Questionnaire
- 5) A quick series of clinical tests of balance and gait including the Mini-Balance Evaluation Systems Test (mini-BEST), the 6-minute walk test, the Activity Specific Balance Scale Test, a Sensorimotor and Vision screen, and the Dynamic Gait Index (DGI).
- 6) A neuropsychological assessment using a brief, targeted battery of test including both paper and pencil and computerized measures. We will perform this in a quiet environment in the Clinical Research Unit (CRU) (room 130), Room 510 (Building 1), or building 103, room 1106, also at the VA Puget Sound Healthcare System.

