## 5.5 Study Evaluations

**Demographics:** Sex, age, height, weight, ethnicity (incl. Hispanic origin), education, year of initial PD diagnosis, co-morbid medical diagnoses, and medications (PD & non-PD).

**Clinical characteristics & quality of life:** The severity of PD motor signs will be quantified using the Movement Disorders Society Unified Parkinson's Disease Rating Scale (MDS-UPDRS). Fall history will be assessed using a questionnaire including the number of recent falls, circumstances, causes, and associated injuries. Physical activity levels will be assessed using the International Physical Activity Questionnaire. Clinical tests of balance and gait will include the Mini-Balance Evaluation Systems Test (mini-BEST), the Activity specific balance confidence scale, a sensorimotor and vision screen, the 6-minute walk test, and the Dynamic Gait Index (DGI). Quality of life questionnaires will include the PDSS-2, PDQ-8, and the ESS.

**Gait Training Intervention:** All 30 individuals will attend a 10-week training program at the physical therapy gym at the VA Puget Sound, consisting of 1-hour sessions, twice a week (**Table 1**). The program will involve light intensity training on a treadmill with special focus on improving gait form for 2 weeks, followed by 8 weeks of monitored, self-controlled moderate to vigorous,

intensity gait training on a treadmill, with verbal cues for gait quality provided regularly throughout the gait training sessions. Adding verbal cues will incorporate declarative (explicit) in addition to procedural (implicit) learning processes. Feedback about the training speed achieved will be provided at the end of each 5-minute block.

**Balance and Walking Assessment: (AIM 1)** Walking will be assessed at the VA RR&D Center Motion Analysis Laboratory in a 1 hour session at 4 time points (**Table 1**): 0 weeks (baseline), 2 weeks (short-term motor learning changes), 10 weeks (long-term motor learning changes, immediately post-training), and 16 weeks (retention of motor learning, follow-up) using a wearable inertial sensor system. Motor learning will be assessed using gait speed during self-paced walking from baseline to 2 weeks (short-term motor learning changes) and from baseline to 10 weeks (long-term motor learning changes).

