Objective spatiotemporal parameters of walking will be measured with the portable APDM Movement Monitoring Solutions system (APDM, Inc.), which uses six inertial sensors attached to the wrists, feet, pelvis, and trunk to quantify body movements during mobility tasks. We have used the APDM inertial sensor system extensively to quantify balance and gait in people with PD and other older adult populations, with data collection completed for >20 people with PD and >90 people with mild cognitive impairment or early AD. Participants will walk back and forth across a 7-m course for one minute. Two trials each will be performed under single-task (walking only) and dual-task walking (walking while performing serial-3 subtractions), allowing us to quantify changes in both straight-line walking and 180 degree turns under conditions of increasing cognitive load. Motor learning will be assessed using the primary outcome of gait speed during straight-line walking under single-task conditions. Therapists will be blinded to the subjects' genotyping status.

**Secondary analyses:** We will also measure retention and transfer of motor learning. Retention of motor learning will be assessed by differences in walking speed from post-training (10 weeks) to follow-up (16 weeks) time points (**Table 1**). Transfer of motor learning from a simple walking task (self-paced straight-line walking on a treadmill) to complex walking tasks (turning, dual-task walking) that are commonly impacted by PD will be assessed by the change in walking speed during complex walking tasks from pre-training to post-training time points.

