## 5.7 Withdrawal of Subjects

This is not a treatment study; withdrawing or being terminated from this study will not have an impact on participant safety. Our recruitment and screening processes are designed to identify individuals who can tolerate 10 weeks of gait training, but a study clinician or the PI may withdraw a participant without their consent if he or she feels that it is not in a participant's best interest to continue in the study or if they are unable to complete the study procedures. For example if the participant develops knee pain that cannot be appropriately managed by decreased training intensity.

All data previously collected from participants who withdraw, or are withdrawn, will be kept and may be used in the study data analysis. Participants may withdraw at any time by informing the Research Coordinator and/or the PI.

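### The two-visit ANOVAs for gait speed use only participants seen at both visits; one four-visit mixed model with named contrasts would also use the partial data the plan keeps

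*Combined protocol and SAP*

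**What the plan says.** Section 5.1 plans "30 Veterans with PD (10 subjects in each the three genotype groups". Section 5.5 names the endpoint: "Motor learning will be assessed using the primary outcome of gait speed during straight-line walking under single-task conditions". It places gait assessments at baseline and 2 weeks, then at "10 weeks (long-term motor learning changes, immediately post-training), and 16 weeks (retention of motor learning, follow-up". Table 1 shows the same four visits.

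Section 5.6 (Aim 1) analyses these visits in pairs. The primary hypothesis uses a repeated-measures ANOVA with "time point (0 weeks, 2 weeks for short-term motor learning; 0 weeks, 10 weeks for long-term motor learning" as the within-person factor. Retention uses a separate one with "time point (10 weeks, 16 weeks follow-up". On covariates the default is "For all analysis, unadjusted models will be used".

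On withdrawal, section 5.7 states: "All data previously collected from participants who withdraw, or are withdrawn, will be kept and may be used in the study data analysis". It allows removal where continuing is not in a participant's interest, "or if they are unable to complete the study procedures". No section says how partial data would enter an analysis, what loss is expected, or how missing visits are handled. The plan also gives no alpha, power or effect size, so there is no stated figure to reproduce.

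**The concern.** With two time points, the group-by-time term compares the change between those two visits across the three genotype groups. Someone with one of the two visits has no change to contribute. Each ANOVA is therefore in effect a complete-pair analysis, although the plan never says so.

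The consequence differs by contrast. A participant who leaves after week 2 is fully used for short-term learning and absent from the long-term and retention tests. Their week-2 value, the only observation on how they responded to training, cannot inform the 0-10 week comparison. With 10 per group, each such loss is 10% of a group. If early response is related to leaving, the remaining participants are a selected sample and the long-term genotype comparison is biased.

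**Working it through.** **Inputs from the documents.** Three non-randomised groups of 10; gait visits at weeks 0, 2, 10 and 16; pairwise ANOVAs; unadjusted by default; partial data retained.

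**Assumed inputs (none are in the documents).** Two-sided 0.05; SD of the 10-week change 0.10 m/s; noncarrier-minus-carrier difference in that change 0.10 m/s; correlation of 2-week and 10-week change 0.5-0.7; 10-30% loss after week 2.

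**Step 1: information lost.** Take noncarriers one SD above both carrier groups. The noncentrality of the three-group F test is n × [(2/3)² + 2 × (1/3)²] = n × 2/3, on 2 and 3n − 3 degrees of freedom.

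| Pairs per group | Noncentrality | df | Power |
|---|---|---|---|
| 10 | 6.67 | 2, 27 | 58% |
| 9 | 6.00 | 2, 24 | 53% |
| 8 | 5.33 | 2, 21 | 47% |
| 7 | 4.67 | 2, 18 | 41% |

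The standard error of noncarriers against pooled carriers is 0.10 × √(1/n + 1/(2n)). That is 0.039 at n = 10 and 0.043 at n = 8. The mixed model recovers only part of this loss. In simulation with random loss its spread was 0.041-0.043 against 0.043 for completers at 20% loss, and 0.044-0.046 against 0.047-0.048 at 30%.

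**Step 2: why bias can go either way.** Write D2 and D10 for the changes to weeks 2 and 10, and suppose the mean of D10 given D2 in group g is a_g + β × D2, with β = correlation × SD(D10)/SD(D2). If leaving depends only on D2, the completers' mean in group g shifts by β × [mean D2 of stayers − mean D2 of everyone in g]. The bias in the genotype difference is the noncarrier shift minus the carrier shift.

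- If leaving is unrelated to D2, or β = 0, the bias is zero.
- If poor early responders leave under the same rule everywhere, and carriers gain less early as hypothesised, the carrier mean is pushed up more and the difference shrinks.
- If such loss occurs only among noncarriers, their mean alone is pushed up and the difference grows.

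**Step 3: size.** Mean estimates with true difference 0.100 m/s, 20% loss and 6,000 simulated trials per scenario:

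| Reason for loss | Completers | Four-visit model |
|---|---|---|
| Random | 0.100 | 0.100 |
| Baseline speed only | 0.100 | 0.100 |
| Poor early response, all groups | 0.094-0.096 | 0.100 |
| Poor early response, noncarriers only | 0.114-0.120 | 0.100-0.101 |
| Unseen week-10 change | 0.084 | 0.088-0.091 |

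Over 10-30% loss, the third row spans about 3-8% attenuation and the fourth 8-26% exaggeration. A separate simulation with a true difference of 0.060 m/s and nominal 10-30% loss of poor early responders gave 0.053-0.055 for completers, an attenuation of (0.060 − 0.055)/0.060 = 8% to (0.060 − 0.053)/0.060 = 12%. The four-visit model gave about 0.059-0.060. When loss depended on the unseen week-10 result, the figures were 0.046-0.052 against 0.050-0.055.

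**Step 4: what the model must look like.** With complete data and group-by-visit means, the unstructured model gives the same contrast estimates as the planned ANOVAs. Three implementation choices matter.

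- *Covariance.* A random intercept forces equal variance on every between-visit change. With assumed unequal change variances, complete data and no true effect, its 0-10 week test rejected 9.4% of the time against 4.9% for the planned test.
- *Test.* A 6-df omnibus test of all four visits lowers power from 59% to 49% at a difference of 0.10 m/s.
- *Inference.* Large-sample inference with maximum-likelihood variance gives 8.8% type I error.

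**The case against.** The strongest reply is that selective loss is conjecture. The documents never say that poor early responders leave. The one example of withdrawal in section 5.7 is knee pain. Training stays light until about the week-2 assessment and becomes harder afterwards, so intolerance may arise later and be unrelated to week-2 gait speed. Screening targets people able to tolerate the programme, and section 5.2 weights payment towards the last two assessments ($50 and $100). The bias is also small against the noise: in the scenario with true difference 0.100 it is 0.004-0.006 m/s against a standard error of about 0.043, roughly a tenth to a seventh.

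All of this stands as a limit on size. It does not alter the fact that the stated tests cannot use the week-2 value for the long-term comparison.

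A reader might infer that the planned analysis necessarily shrinks the genotype effect and that a mixed model removes this at no cost. The documents do not support that. They give no dropout rate or mechanism, and the bias may be nil, towards zero or away from it. Removal needs missing at random given the observed gait speeds, whereas removal for inability to complete procedures could depend on outcomes never observed. Nor is there a contradiction between sections 5.6 and 5.7: the latter only permits use of the data, and the 0-2 week test does use them.

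**Conclusion.** The point holds in a limited form. Each gait-speed ANOVA is a complete-pair analysis, and early data kept from participants who later withdraw are idle in the 0-10 and 10-16 week tests. The certain consequence is some loss of precision, of which a four-visit model recovers a modest part. The conditional consequence is bias in the long-term genotype comparison. It ranges from none, through about 3-12% attenuation under a common early-response mechanism, to 8-26% exaggeration if selective loss is confined to noncarriers. These sizes rest wholly on assumed effects, SDs, correlations and loss rates. Where loss depends on unseen outcomes the model narrows the bias but leaves some: 9-12% remains of about 16% in the 20% loss scenario. This is a cheap improvement that should be made; it does not invalidate the plan.

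**What to change.** In section 5.6, Aim 1, replace the pairwise gait-speed ANOVAs with one REML linear mixed model:

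- all available values at weeks 0, 2, 10 and 16 as outcomes, with a mean for each genotype group at each visit;
- unstructured covariance, not a random intercept alone, and small-sample degrees of freedom;
- the genotype comparisons of change over 0-2, 0-10 and 10-16 weeks prespecified as named contrasts, in place of any omnibus four-visit test.

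Baseline stays an outcome, so the default of unadjusted comparisons between non-randomised groups is preserved.

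State the missing-at-random assumption, say that retained data from withdrawn participants enter this model, and report missing visits and reasons by genotype group. A sensitivity analysis for loss that depends on unseen outcomes would be a useful addition.

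The cost is analysis wording only: no extra visits, participants or measurements. The small downside is a covariance matrix with 4 × 5/2 = 10 parameters estimated from 30 people, which is why the small-sample correction is needed.

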**Gap in knowledge to be addressed.** PD is a heterogeneous disorder with considerable inter-individual differences in clinical features, disease course, and treatment response, which can be due to disease processes and other clinical variables, but also by other factors such as genetics. Currently, rehabilitation approaches do not take into account an individual's genetic profile, which may impact learning and therefore mediate the response to rehabilitation. Two genes that have been shown to play an important role in motor learning are the genes coding for brain-derived neurotrophic factor (*BDNF*) and apolipoprotein E (*APOE*). The *BDNF* protein is involved in neuronal survival and synaptic plasticity (34) and a variant in the *BDNF* gene (Val66Met), carried by approximately 30% of European-Americans has been associated with greater error in motor learning in healthy individuals (35) and appears to impact rates of motor learning on a locomotor adaptation task in individuals with cerebrovascular accidents (36). This variant results in 18 to 30% less activity-dependent secretion of the *BDNF* protein (37). On the other hand, the *APOE* gene encodes a glycoprotein that plays an important role in neuronal repair and synaptic remodeling. Genetic variation in this gene (*APOE-ε4*) is a well-known risk factor for AD, but has also been associated with motor decline (explained mostly by a loss in muscle strength) (38) and abnormal gait (shorter stride length and greater dual-task related disturbances in stride length) (39), in the elderly. Recently, we and others have shown that the *APOE-ε4* allele is associated with poorer performance on specific cognitive domains in PD (40). Therefore, understanding the effect of genetic variants on the physical and cognitive improvement in response to training is an essential first step to investigate this relationship.

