Secondary walking measures to inform the mechanisms underlying any gait changes will assess specific gait domains (43-45) and will include step time, step time variability, step time asymmetry, and arm swing range of motion. These gait measures will be calculated in both single-task and dual-task walking conditions. In the dual task condition, performance of the serial-3 subtraction task will be audio recorded and the number of responses (correct and incorrect) will be tallied offline. Cognitive task performance will be measured as the correct response rate (number of correct responses per second), with number of correct responses and percent of correct responses (number of correct responses / total number of responses \* 100%). Turns will be quantified using peak turning velocity as the primary measure, with turn time and number of steps required to turn as secondary measures for turning.

**Neuropsychological Assessment: (AIM 2)** Cognitive performance will be measured at baseline (0 weeks) and post-training (10 weeks) (**Table 1**) using a brief, targeted battery aimed at assessing learning/memory, executive function, attention and processing speed. The battery will include both paper and pencil and computerized measures, and is approximately 45 minutes in length. When needed, we will minimize learning effects by using different versions of the same test pre- and post-training program. The battery includes:

- 1) **Story recall (46):** This measure of episodic verbal memory consists of an auditory presentation of a brief story, followed by immediate and delayed recall conditions.

Multiple validated equivalent versions of this measure are available and will be presented in a counterbalanced, randomized order.

- 2) Frontal Assessment Battery (47): This battery assesses a broad sampling of executive functions (abstract reasoning, phonemic verbal fluency, motor programming, interference, response inhibition) with minimal subject and time burden. It has been used in clinical trials and in pre- and post-intervention designs without apparent practice effects (48, 49).
- 3) Flanker Inhibitory Control and Attention Test (50): This computerized task is part of the NIH Toolbox and is derived from the Attention Network Test. It examines the participant's ability to inhibit visual attention to irrelevant stimuli.

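### Transfer to dual-task walking is judged on gait speed alone; the change in the subtraction score from the same trials is not analysed, so a genotype difference in task priority could be read as a difference in transfer

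*Combined protocol and SAP*

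**What the plan says.** All references are to the combined protocol and SAP.

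- **Outcome for transfer.** Section 5.6, Aim 1, uses a repeated-measures ANOVA with time point (weeks 0 and 10) and genetic group, "to examine changes in gait speed for dual-task walking and peak turning velocity for turning while walking". Section 5.5 agrees: transfer "will be assessed by the change in walking speed during complex walking tasks from pre-training to post-training time points".
- **The task.** "Two trials each will be performed under single-task (walking only) and dual-task walking (walking while performing serial-3 subtractions"). The text describes no seated subtraction trial and no instruction on which task to put first.
- **What is recorded.** While participants walk and subtract, "performance of the serial-3 subtraction task will be audio recorded and the number of responses (correct and incorrect) will be tallied offline". Section 5.5 then fixes the scoring: "Cognitive task performance will be measured as the correct response rate (number of correct responses per second"), with number and percent correct alongside.
- **How 5.6 uses the score.** There are two uses. The first is a baseline comparison: "Descriptive analyses at baseline will be used to examine participant characteristics and demographic variables and compare them across the sample and by genotype", in a list that includes cognitive task performance. The second is a conditional covariate, for use where the genotype groups are found to differ: "We will consider adjusting for age, height, cognitive task performance (for dual-task) or global cognition if any of these factors are shown to be different". Models are otherwise unadjusted.
- **What is absent.** No section names an analysis of the week 0 to week 10 change in the subtraction score. The Aim 2 battery lists seven tests, and serial subtraction is not among them. The other dual-task measures in 5.5 (step time, its variability and asymmetry, arm swing) are all gait measures.

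**The concern.** Walking while subtracting has two outputs, and a participant can improve one by giving up some of the other. If only walking speed is tested, a participant who walks faster because they attend less to the sums looks the same as one whose walking has become more automatic.

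A change in priority over training is plausible here. Section 2.0 describes cognitive cueing as instruction to concentrate on walking, and sections 5.1 and 5.5 give verbal cues for gait quality throughout training. A difference between genotype groups is also conceivable on the protocol's own premises: carriers are expected to learn less, and section 2.0 links APOE-ε4 in the elderly with "shorter stride length and greater dual-task related disturbances in stride length".

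At stake is the reading of one component of a secondary hypothesis. A group that drops sums and speeds up would appear to transfer better. A group that holds its speed and answers more sums would appear to gain nothing.

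**Working it through.** **1. What can be reproduced.** The documents state no alpha, power, effect size, SD or dropout for this hypothesis. The only figure to check is the sample size, 3 × 10 = 30. The following is therefore an illustration on assumed values.

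**2. Model.** With two time points, the group-by-time test equals an F test on change scores with 2 and 27 degrees of freedom. Assumptions, none from the documents:

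- two-sided alpha 0.05, 10 per group, no true motor transfer in any group;
- the change in subtraction score has SD 1 within each group, and its mean is −s in the non-carrier group and 0 in the two carrier groups;
- speed change = −k × (change in subtraction score) + noise of SD 1;
- baseline subtraction scores have the same distribution in all groups and are unrelated to change.

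Mean speed change is then ks in one group and 0 in the other two, with variance 1 + k². The squared deviations of (ks, 0, 0) from their mean sum to (2/3)k²s², so the noncentrality is

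λ = 10 × (2/3) × k²s² / (1 + k²).

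For k = 1 and s = 1, λ = 6.667 / 2 = 3.33. Against the critical value F(2, 27) = 3.354, this gives rejection in 32.0% of trials.

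**3. Results.** Each row comes from 4,000 simulated trials, with the noncentral F value as a check. Entries are the percentage of trials significant at 0.05.

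| k | s | Speed, unadjusted (simulated) | Speed, noncentral F | Speed, baseline-triggered covariate | Speed, change in score in model | Subtraction score itself |
|---|---|---|---|---|---|---|
| 0.5 | 0 | 5.0 | 5.0 | 5.0 | 5.0 | 4.8 |
| 0.5 | 0.5 | 7.8 | 7.3 | 7.8 | 5.4 | 18.7 |
| 0.5 | 1.0 | 14.6 | 15.0 | 14.4 | 5.0 | 56.7 |
| 0.5 | 1.5 | 30.2 | 29.1 | 30.0 | 4.4 | 91.6 |
| 1.0 | 0 | 5.1 | 5.0 | 5.0 | 5.0 | 5.5 |
| 1.0 | 0.5 | 11.6 | 11.1 | 11.5 | 4.4 | 17.6 |
| 1.0 | 1.0 | 31.8 | 32.0 | 31.8 | 4.8 | 57.7 |
| 1.0 | 1.5 | 63.0 | 63.5 | 62.6 | 4.8 | 91.3 |

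The covariate column reads the plan's conditional adjustment as a baseline covariate used when baseline scores differ at p < 0.05. That happens in 4.3% to 5.7% of trials, so the result hardly moves. Groups that are alike at week 0 do not trigger it, however far apart they are at week 10. The next column shows where the excess comes from. It is not a recommended analysis, because it conditions on something measured after training.

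**4. The reverse error.** Suppose non-carriers truly gain d more than carriers, and both carrier groups shift attention enough to add ks = d to their speed. The three mean changes are then equal, λ = 0, and a real difference is found only at the 5% error rate.

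**5. A common shift.** If all three groups shift by 1 SD with k = 1, the group-by-time test is significant in 5.4% of trials, so the genotype comparison is not biased. The time effect is significant in 96% of trials, although no motor transfer has occurred.

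**The case against.** The strongest reply has four parts.

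- **The covariate may not be baseline-only.** Section 5.6 does not say at which visit cognitive task performance would be measured for adjustment; only the descriptive comparison is labelled baseline. Section 5.1 repeats the quantitative assessment at visits 4, 20 and 21, so a covariate taken at each visit is a possible reading and would meet part of the problem. This stands as an ambiguity. A reader might infer that the plan restricts the score to baseline use, but the text does not say so. Nor does it say the opposite, and the adjustment remains optional.
- **The plan is brief about every mechanistic measure.** Section 5.6 names no model for step time, arm swing or turn time either, and the subtraction score is collected with its scoring fixed in advance. That is fair. The score differs from those measures, however, because it is the other half of the task on which transfer is judged.
- **A dual-task gain equal to the single-task gain is not an artefact.** A reader might infer that such a gain only repeats the primary result. Take assumed speeds of 1.10 to 1.20 m/s (single-task) and 0.95 to 1.05 m/s (dual-task). Both rise by 0.10 m/s, which is 0.10/1.10 = 9.1% and 0.10/0.95 = 10.5%. Dual-task cost moves only from 0.15/1.10 = 13.6% to 0.15/1.20 = 12.5%. Sections 3.0 and 5.6 define transfer as carry-over from the trained task to complex walking, and on that definition this is full transfer. Dual-task cost measures interference, which is a different quantity. This part of the reply stands.
- **A differential shift is assumed, not shown.** The cited APOE-ε4 association concerns stride length in the elderly. It says nothing about task priority, about its change with training, or about BDNF. The simulation shows what could happen, not how likely it is. This also stands.

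**Conclusion.** The point holds as an omission in the analysis. Sections 5.5 and 5.6 judge dual-task transfer on walking speed alone. The one recorded measure that would reveal a trade-off has no analysis of change, and a covariate triggered by a baseline difference would not supply one.

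The possible distortion of the genotype test runs from about 8% to 63% false positives against 5%, over assumed shifts of 0.5 to 1.5 SD in one group and assumed coupling k of 0.5 to 1.0. It arises only if the trade-off differs between genotype groups. If all groups shift alike, only the time effect is affected.

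A reader might infer that any gain in dual-task speed is suspect, or that Aim 1 as a whole is compromised. The documents support neither. The issue touches one component of one secondary hypothesis; turning is measured separately, and the primary outcome, single-task gait speed, is unaffected. It is a worthwhile and inexpensive correction, not a flaw in the design.

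**What to change.** In section 5.6, under the transfer hypothesis:

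1. Analyse the week 0 to week 10 change in correct response rate by genetic group, with the same repeated-measures model as dual-task gait speed.
2. Report the two outcomes side by side as estimates with confidence intervals for each group and for the differences between groups.
3. Interpret dual-task transfer from the two together. Describe a speed gain accompanied by a lower response rate as a possible trade-off, not as clear transfer.
4. State the visit at which cognitive task performance is measured if used as a covariate, and state that adjustment triggered by a baseline difference does not address a change in task priority.
5. Optionally, show the change in dual-task cost of gait speed, (single − dual)/single, as a descriptive measure of interference and not as the definition of transfer.

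Do not set a pass/fail rule on the response rate. On point estimates, a group with no true change would show a fall about half the time. A rule requiring a significant group difference would detect a 0.5 SD shift in only about 18% of trials and a 1 SD shift in about 57% (last column of the table). For the same reason, a non-significant change should not be taken as evidence that there was no trade-off.

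The cost is one more secondary analysis of data already planned, with no new visit, test or staff. It will be imprecise at 10 per group, and the conclusion on transfer becomes somewhat more cautious. Without a seated subtraction trial, practice or a true cognitive gain could still mask a shift in priority, and the report should say so.
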